3. OBJECTIVES AND ENDPOINTS

Table 3 Study objectives

Primary Objective:	Endpoint/Variable:
To describe safety profile of durvalumab in combination with platinum–etoposide as first-line treatment for patients with ES-SCLC and also as monotherapy maintenance treatment.	Incidence of grade ≥ 3 AEs Incidence of imAE

Secondary Objective:	Endpoint/Variable:
To describe effectiveness of durvalumab in combination with platinum–etoposide as first-line treatment for patients with ES-SCLC.	Progression Free Survival (PFS). PFS rate at 6 months and at 1 year (PFS6, PFS12). Objective Response Rate (ORR): using site investigator assessments according to RECIST 1.1. Duration of Response (DoR) DoR at 1 year (DoR12). Time to Treatment Discontinuation (TTD). Overall Survival (OS). The OS rate at 6, 12 and 18 months. Time to event endpoints measured as time from first Durvalumab dose.
To describe the impact of durvalumab in combination with platinum–etoposide as first-line treatment for patients with ES-SCLC on patients’ disease-related symptoms and Health Related Quality of Life (HRQoL) and (PROs).	Changes in vital signs, physical findings, and clinical laboratory results during and following study treatment administration Change from baseline in European Organisation for Research and Treatment of Cancer Quality of Life Questionnaire Core 30 items (EORTC QLQ-C30). Change from baseline in European Organisation for Research and Treatment of Cancer Quality of Life Questionnaire-Lung Cancer 13 (EORTC QLQ-LC13).
To describe health care resources use related to management of ES-SCLC patients treated with durvalumab in combination with platinum–etoposide as first-line treatment.	Changes from baseline in PRO-CTCAE. 
- Number and length of hospitalizations- Number of visits to oncology service- Number of emergency visits- Number of outpatient visits- Number of imaging tests- Number of biopsy-related procedures- Treatment dose, duration, number of cycles

Secondary Objective:	Endpoint/Variable:
To describe effectiveness of durvalumab in combination with platinum–etoposide as first-line treatment for patients with ES-SCLC.	Progression Free Survival (PFS). PFS rate at 6 months and at 1 year (PFS6, PFS12). Objective Response Rate (ORR): using site investigator assessments according to RECIST 1.1. Duration of Response (DoR) DoR at 1 year (DoR12). Time to Treatment Discontinuation (TTD). Overall Survival (OS). The OS rate at 6, 12 and 18 months. Time to event endpoints measured as time from first Durvalumab dose.
To describe the impact of durvalumab in combination with platinum–etoposide as first-line treatment for patients with ES-SCLC on patients’ disease-related symptoms and Health Related Quality of Life (HRQoL) and (PROs).	Changes in vital signs, physical findings, and clinical laboratory results during and following study treatment administration Change from baseline in European Organisation for Research and Treatment of Cancer Quality of Life Questionnaire Core 30 items (EORTC QLQ-C30). Change from baseline in European Organisation for Research and Treatment of Cancer Quality of Life Questionnaire-Lung Cancer 13 (EORTC QLQ-LC13).
To describe health care resources use related to management of ES-SCLC patients treated with durvalumab in combination with platinum–etoposide as first-line treatment.	Changes from baseline in PRO-CTCAE. 
- Number and length of hospitalizations- Number of visits to oncology service- Number of emergency visits- Number of outpatient visits- Number of imaging tests- Number of biopsy-related procedures- Treatment dose, duration, number of cycles

Exploratory Objective:	Endpoint/Variable:
-------------------------------	---------------------------

Secondary Objective:

Endpoint/Variable:

To describe effectiveness of durvalumab in combination with platinum–etoposide as first-line treatment for patients with ES-SCLC.

Progression Free Survival (PFS).
PFS rate at 6 months and at 1 year (PFS6, PFS12).
Objective Response Rate (ORR): using site investigator assessments according to RECIST 1.1.
Duration of Response (DoR)
DoR at 1 year (DoR12).
Time to Treatment Discontinuation (TTD).
Overall Survival (OS).
The OS rate at 6, 12 and 18 months.

To describe the impact of durvalumab in combination with platinum–etoposide as first-line treatment for patients with ES-SCLC on patients’ disease-related symptoms and Health Related Quality of Life (HRQoL) and (PROs).

Time to event endpoints measured as time from first Durvalumab dose.
Changes in vital signs, physical findings, and clinical laboratory results during and following study treatment administration
Change from baseline in European Organisation for Research and Treatment of Cancer Quality of Life Questionnaire Core 30 items (EORTC QLQ-C30).
Change from baseline in European Organisation for Research and Treatment of Cancer Quality of Life Questionnaire-Lung Cancer 13 (EORTC QLQ-LC13).

To describe health care resources use related to management of ES-SCLC patients treated with durvalumab in combination with platinum–etoposide as first-line treatment.

Changes from baseline in PRO-CTCAE.

- Number and length of hospitalizations
- Number of visits to oncology service
- Number of emergency visits
- Number of outpatient visits
- Number of imaging tests
- Number of biopsy-related procedures
- Treatment dose, duration, number of cycles

[REDACTED]

[REDACTED]

[REDACTED]

Once the eligible participant has given the informed consent to be included at the program, study variables apart from those that will be used to assess the objectives, will include at least the following:

- **Demographic characteristics:** age, gender, race/ethnicity, smoking status, family history of cancer.
- **Clinical characteristics:** SCLC stage, tumor site and histology, number and location of metastases including brain metastases, presence of other primary malignancy at diagnosis, performance status according to the ECOG scale.

4. STUDY DESIGN

4.1 Overall design

For an overview of the study design see Figure 1, Section 1.3. For details on treatments given during the study, see Section 6.1 Treatments Administered.

For details on what is included in the efficacy and safety endpoints, see Section 3 Objectives and Endpoints.

This is a Phase IIIb, interventional, single arm, multicentre study to evaluate safety, effectiveness, use of resources and patient reporting outcomes in patients with ES-SCLC treated with durvalumab in combination with platinum–etoposide as first-line treatment in Spain.

This study will include approximately 85 eligible patients at participating Spanish sites.

Durvalumab will be concurrently administered with first-line chemotherapy (EP) on an every 3 week (q3w) schedule for 4 to 6 cycles, and will continue to be administered as monotherapy post-chemotherapy on an every 4 week (q4w) schedule until confirmed progressive disease (PD) or unacceptable toxicity.

Prophylactic cranial irradiation (PCI) is allowed in patients showing complete or partial responses after the durvalumab + EP combination cycles, at the discretion of the investigator according to their local clinical practice.

Assessments will be conducted as indicated in Table 2 and Table 3.

Tumor assessments will be performed at Screening as baseline with follow-ups following local standard practice, but at least with a maximum interval of 12 weeks. It is recommended that on-study tumor assessments occur at Week 9 \pm 1 week from the date of inclusion for the first 12-18 weeks (during durvalumab + EP, relative to the C1D1), and then every 8 \pm 1 weeks until confirmed objective disease progression (please refer to Appendix E).

4.2 Scientific rationale for study design

CASPIAN was a randomized, open-label, multi-centre, global, Phase III trial in the first line treatment of patients with ES-SCLC (NCT03043872). Durvalumab + EP demonstrated a statistically significant and clinically meaningful improvement in overall survival versus EP alone, with an HR of 0.73 (95% CI 0.59–0.91; p=0.0047). Overall survival benefit was observed across all clinically relevant patient subgroups.

The overall safety profile in CASPIAN was similar between the two groups, with similar frequencies of grade 3 or 4 adverse events, adverse events leading to discontinuation, and adverse events leading to death. The most common adverse events were haematological toxicities. Immune-mediated adverse events were mostly low grade and manageable with standard treatment guidelines and were numerically higher in the durvalumab plus platinum–etoposide group, and consistent with the known safety profile of durvalumab.

This phase IIIb single arm study, is supported by the available clinical safety and efficacy data provided by CASPIAN randomized, open-label, phase 3 trial compared to other currently available treatment options that offer a limited life expectancy. It is expected that durvalumab in combination with etoposide and either carboplatin or cisplatin chemotherapy followed by durvalumab monotherapy, will be approved by the EMA during 2020. This trial will provide an opportunity to further evaluate the safety profile and efficacy of durvalumab + EP in patient population that is reflective of real-world clinical practice, including patients with ECOG performance status 2 who have not been included in pivotal studies of immunotherapy in this disease setting.

4.3 Justification for dose

4.3.1.1 Durvalumab dose rationale

A durvalumab dose of 20 mg/kg q4w is supported by in vitro data, pre-clinical activity, clinical PK/pharmacodynamics, biomarkers, and activity data from Study CD-ON-MEDI4736-1108 (hereafter referred to as Study 1108) in patients with advanced solid tumors and from a Phase I study performed in Japanese patients with advanced solid tumor (D4190C00002).

PK/Pharmacodynamic data

Based on available PK/pharmacodynamic data from ongoing Study 1108 with doses ranging from 0.1 to 10 mg/kg q2w or 15 mg/kg q3w, durvalumab exhibited non-linear (dose-dependent) PK consistent with target-mediated drug disposition. The PK approached linearity at ≥ 3 mg/kg q2w, suggesting near complete target saturation (membrane-bound and sPD-L1), and further shows that the durvalumab dosing frequency can be adapted to a particular regimen given the linearity seen at doses higher than 3 mg/kg. The expected half-life with doses ≥ 3 mg/kg q2w is approximately 21 days. A dose-dependent suppression in peripheral sPD-L1 was observed over the dose range studied, consistent with engagement of durvalumab with PD-L1. A low level of

immunogenicity has been observed. No patients have experienced immune-complex disease following exposure to durvalumab. (For further information on immunogenicity, please see the current durvalumab IB).

A population PK model was developed using the data from Study 1108 (doses=0.1 to 10 mg/kg q2w or 15 mg/kg q3w; Fairman et al 2014). Multiple simulations indicate that a similar overall exposure is expected following both 10 mg/kg q2w and 20 mg/kg q4w regimens, as represented by AUC_{ss} (4 weeks). Median $C_{max,ss}$ is expected to be higher with 20 mg/kg q4w (~1.5 fold) and median $C_{trough,ss}$ is expected to be higher with 10 mg/kg q2w (~1.25 fold). Clinical activity with the 20 mg/kg q4w dosing regimen is anticipated to be consistent with 10 mg/kg q2w with the proposed similar dose of 20 mg/kg q4w expected to (a) achieve complete target saturation in majority of patients; (b) account for anticipated variability in PK, pharmacodynamics, and clinical activity in diverse cancer populations; (c) maintain sufficient PK exposure in case of ADA impact; and (d) achieve PK exposure that yielded maximal antitumor activity in animal models.

Given the similar area under the serum drug concentration-time curve (AUC) and modest differences in median peak and trough levels at steady state, the observation that both regimens maintain complete sPD-L1 suppression at trough, and the available clinical data, the 20 mg/kg q4w and 10 mg/kg q2w regimens are expected to have similar efficacy and safety profiles, supporting further development with a dose of 20 mg/kg q4w.

Clinical data

Refer to the current durvalumab IB for a complete summary of clinical information including safety, efficacy, and PK at the 20 mg/kg q4w regimen.

4.3.1.2 Rationale for fixed dosing

A population PK model was developed for durvalumab using monotherapy data Study 1108 (N=292; doses= 0.1 to 10 mg/kg q2w or 15 mg/kg q3w; solid tumors). Population PK analysis indicated only minor impact of body weight (WT) on the PK of durvalumab (coefficient of ≤ 0.5). The impact of body WT-based (10 mg/kg q2w) and fixed dosing (750 mg q2w) of durvalumab was evaluated by comparing predicted steady state PK concentrations (5th, median, and 95th percentiles) using the population PK model. A fixed dose of 750 mg was selected to approximate 10 mg/kg (based on median body WT of ~75 kg). A total of 1000 patients were simulated using body WT distribution of 40 to 120 kg. Simulation results demonstrate that body WT-based and fixed dosing regimens yield similar median steady state PK concentrations with slightly less overall between-patient variability with fixed dosing regimen.

Similar findings have been reported by others (Narwal et al 2013, Ng et al 2006, Wang et al 2009, Zhang et al 2012). Wang and colleagues investigated 12 monoclonal antibodies and found that fixed and body size-based dosing perform similarly, with fixed dosing being better for 7 of 12 antibodies (Wang et al 2009). In addition, they investigated 18 therapeutic proteins and peptides and showed that fixed dosing performed better for 12 of 18 in terms of reducing the between-patient variability in PK/pharmacodynamic parameters (Zhang et al 2012).

A fixed dosing approach is preferred by the prescribing community due to ease of use and reduced dosing errors. Given expectation of similar PK exposure and variability, AstraZeneca considered it feasible to switch to fixed dosing regimens. Based on average body WT of 75 kg, a fixed dose of 1500 mg q4w durvalumab (equivalent to 20 mg/kg q4w) is included in the current study.

4.3.1.3 Rationale for durvalumab + EP dosing regimen

The dose and schedule of durvalumab proposed for this trial is consistent with that employed in the Phase III CASPIAN trial: a fixed dose of 1500 durvalumab Q3W while administered with chemotherapy followed by a fixed dose of 1500 mg durvalumab Q4W while administered as monotherapy maintenance until disease progression (Paz-Ares 2019). Likewise, the dose and schedule of etoposide and either carboplatin or cisplatin are consistent with those employed in the phase III CASPIAN trial as well as clinical practice guidelines (Paz-Ares 2019).

This trial will allow up to a maximum of 6 cycles of durvalumab + EP to be administered Q3W. While the CASPIAN trial allowed a maximum of 4 doses of durvalumab + EP, clinical practice guidelines have recommended between 4-6 doses of chemotherapy for treatment of ES SCLC (NCCN, ESMO). In the CASPIAN trial, 57% of patients in the control arm received 6 cycles of EP (Paz-Ares 2019), reflecting the importance of flexibility when determining the actual number of cycles of chemotherapy in clinical practice and the need to obtain safety data on the use of up to 6 cycles of durvalumab + EP. Therefore, this trial will allow up to 6 cycles of Durvalumab + EP.

4.4 End of study definition

The end of study is defined as the last expected visit/contact of the last patient undergoing the study.

A patient is considered to have completed the study when he/she has completed his/her last scheduled visit.

Patients may be withdrawn from the study if the study itself is stopped. The study may be stopped if, in the judgment of AstraZeneca, study patients are placed at undue risk because of clinically significant findings.

See Appendix A 6 for guidelines for the dissemination of study results.

5. STUDY POPULATION

Prospective approval of protocol deviations to recruitment and enrolment criteria, also known as protocol waivers or exemptions, is not permitted.

Each patient should meet all of the inclusion criteria and none of the exclusion criteria for this study in order to be assigned/randomized to a study intervention. Under no circumstances can there be exceptions to this rule. Patients who do not meet the entry requirements are screening failures, refer to section 5.4.

In this protocol, “enrolled” patients are defined as those who sign informed consent. For procedures for withdrawal of incorrectly enrolled patients see Section 7.3.

5.1 Inclusion criteria

Patients are eligible to be included in the study only if all of the following inclusion criteria and none of the exclusion criteria apply:

Informed consent

1. Capable of giving signed informed consent which includes compliance with the requirements and restrictions listed in the informed consent form (ICF) and this protocol.
2. Provision of signed and dated, written informed consent obtained from the patient/legal representative prior to performing any protocol-related procedures. The ICF process is described in Appendix A 3.

Age

3. Male or female ≥ 18 years at the time of screening.

Type of patient and disease characteristics

4. Patients must have histologically- or cytologically-documented extensive-stage SCLC (stage IV [T any, N any, M1a/b/c] or with T3-4 due to multiple lung nodules that are too extensive or have tumor/nodal volume that is too large to be encompassed in a tolerable radiation plan, according to American Joint Committee on Cancer Stage, 8th edition).
 - a. Patients who had received chemoradiotherapy for LS-SCLC and have experienced a treatment-free interval of at least 6 months since last chemotherapy, radiotherapy, or chemoradiotherapy cycle, can be included under investigator criteria.
 - b. Patients may be included if they either do not have brain metastases, or have brain metastases that are asymptomatic, or have brain metastases that have been treated at least 2 weeks prior to study treatment and are currently receiving 10 mg/day or less of prednisone or equivalent. Patients with suspected brain metastases at screening should have a CT/MRI of the brain prior to enrollment.
5. Patients must be considered suitable to receive a platinum-based chemotherapy regimen as 1st line treatment for ES-SCLC. Chemotherapy must contain either cisplatin or carboplatin in combination with etoposide.
6. World Health Organization (WHO)/Eastern Cooperative Oncology Group (ECOG) Performance Status of 0-2 at enrolment/

- a. Note: a maximum of 30% of total patients with PS2 will be allowed; once this limit is met, additional enrolled patients must have PS 0-1.
7. At least 1 lesion, not previously irradiated, that can be accurately measured at baseline as ≥ 10 mm in the longest diameter (except lymph nodes which must have a short axis ≥ 15 mm) with computed tomography (CT) or magnetic resonance imaging (MRI) and that is suitable for accurate repeated measurements as per RECIST 1.1 guidelines.
8. No prior exposure to immune-mediated therapy for cancer including, but not limited to, other anti-CTLA-4, anti-PD-1, anti-PD-L1, and anti-programmed cell death ligand 2 (anti-PD-L2) antibodies.
9. Adequate hematologic and organ function, defined by the following laboratory results obtained within 14 days prior to first Durvalumab dose:
 - a. ANC ≥ 1500 cells/ μ L without granulocyte colony-stimulating factor support
 - b. Platelet count $\geq 100,000$ / μ L without transfusion
 - c. Hemoglobin ≥ 9.0 g/dL
 - d. INR or aPTT $\leq 1.5 \times$ upper limit of normal (ULN); This applies only to patients who are not receiving therapeutic anticoagulation; patients receiving therapeutic anticoagulation should be on a stable dose.
 - e. AST and ALT $\leq 2.5 \times$ ULN, with the following exceptions: Patients with documented liver metastases: AST and/or ALT $\leq 5 \times$ ULN; Patients with documented liver or bone metastases: alkaline phosphatase $\leq 5 \times$ ULN.
 - f. Serum bilirubin $\leq 1.5 \times$ ULN; Patients with known Gilbert disease who have serum bilirubin level $\leq 3 \times$ ULN may be enrolled.
 - g. Measured or calculated creatinine clearance: >60 mL/min for patients on cisplatin and >45 mL/min for patients on carboplatin, as determined by Cockcroft-Gault (using actual body weight):

Males

$$\text{Creatinine CL} = \frac{\text{Weight (kg)} \times (140 - \text{Age})}{72 \times \text{serum creatinine (mg/dL)}} \text{ (mL/min)}$$

Females:

$$\text{Creatinine CL} = \frac{\text{Weight (kg)} \times (140 - \text{Age})}{72 \times \text{serum creatinine (mg/dL)}} \times 0.85 \text{ (mL/min)}$$

10. Evidence of post-menopausal status or negative urinary or serum pregnancy test for female pre-menopausal patients. Women will be considered post-menopausal if they have

been amenorrheic for 12 months without an alternative medical cause. For women of childbearing potential: agreement to remain abstinent (refrain from heterosexual intercourse) or use contraceptive methods that result in a failure rate of < 1% per year during the treatment period and for at least 90 days after the last dose of study treatment. For men: agreement to remain abstinent (refrain from heterosexual intercourse) or use contraceptive measures.

11. Life expectancy of at least 12 weeks.

Weight

12. Body weight >30 kg.

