8.1 Efficacy assessments

This study will evaluate the efficacy of durvalumab + EP as secondary endpoints, in terms of OS, OS rates at 6, 12 and 18 months, as well as PFS, PFS rate at 6 and 12 months from inclusion, ORR, DoR, Time to Treatment Discontinuation and DCR, which will be derived (by AstraZeneca) using Investigator RECIST 1.1 assessments.

Tumor assessments utilize images from CT (preferred) or MRI, each preferably with IV contrast, of the chest and abdomen (including the entire liver and both adrenal glands), collected during screening/baseline and at regular (follow-up) intervals during study treatment. Any other areas of disease involvement should be additionally imaged based on the signs and symptoms of individual patients.

It is important to follow the tumor assessment schedule as closely as possible (refer to the SoAs). If an unscheduled assessment is performed (eg, to investigate clinical signs/symptoms of progression) and the patient has not progressed, every attempt should be made to perform the subsequent assessments at the next scheduled visit. Treatment continues until clinical progression/deterioration or confirmed radiological progression (refer to 0E), and

scanning/tumor assessments continue throughout treatment until RECIST 1.1-defined radiological progression plus an additional follow-up scan (if clinically feasible).

The RECIST 1.1 guidelines (0E) provide a method of assessment of change in tumor burden in response to treatment. Screening/Baseline imaging should be performed no more than 28 days before start of study treatment, and ideally should be performed as close as possible to and prior to the start of study treatment. The RECIST 1.1 assessments of baseline images identify Target Lesions (TLs) (defined as measurable) and Non-Target Lesions (NTLs). On-study images are evaluated for TLs and NTLs chosen at baseline, and for New Lesions (NLs) when they appear. This allows determination of follow-up TL response, NTL lesion response, the presence of unequivocal NLs, and overall timepoint responses (CR, PR, SD, PD, or Not Evaluable [NE]).

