Not evaluable (NE)	Only relevant when 1 or some of the NTLs were not assessed and, in the Investigator’s opinion, they are not able to provide an evaluable overall NTL assessment at this visit. Note: For patients without TLs at baseline, this is relevant if any of the NTLs were not assessed at this visit and the progression criteria have not been met.
Not applicable (NA)	Only relevant if no NTLs present at baseline

CR Complete response; NE Not evaluable; NTL Non-target lesion; PD Progression of disease; TL Target lesion.

RECIST 1.1 NL identification at follow-up

Details, including the imaging modality, the date of scan, and the location of any NLs will also be recorded in the case report form. The presence of 1 or more NLs is assessed as progression. The finding of a NL should be unequivocal, ie, not attributable to differences in scanning technique, change in imaging modality, or findings thought to represent something other than tumor. If a NL is equivocal, for example because of its small size, the treatment and tumor assessments should be continued until the previously (pre-existing) new lesion has been assessed as unequivocal at a follow-up visit, and then the progression date should be declared using the date of the initial scan when the NL first appeared.

A lesion identified at a follow-up assessment in an anatomical location that was not scanned at baseline is considered a NL and will indicate disease progression.

RECIST 1.1 evaluation of overall visit response at follow-up

Derivation of overall visit response as a result of the combined assessment of TLs, NTLs, and NLs uses the algorithm shown in Table 18.

Table 18 RECIST 1.1 overall visit response

Target Lesions	Non-Target Lesions	New Lesions	Overall visit response
CR	CR	No	CR
CR	NA	No	CR
NA	CR	No	CR
CR	Non CR/Non PD	No	PR
CR	NE	No	PR
PR	Non PD or NE or NA	No	PR
SD	Non PD or NE or NA	No	SD
NA	Non-CR/Non-PD	No	SD (non-CR/non-PD)
NE	Non PD or NE	No	NE
NA	NE	No	NE
NA	NA	No	NED
PD	Any	Yes or No	PD
Any	PD	Yes or No	PD
Any	Any	Yes	PD

^a Non-CR/Non-PD for Overall Response if only non-target lesions (no TLs) are present at baseline.

Note: An overall assessment of Complete Response (all other disease disappears/reverts to normal) would be changed to Partial Response if ascites remains present radiologically.

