#### **4.3.3 Cancer history & Performance status**

The following cancer history data will be described for the for the Intent-to-treat (ITT) population.

- WHO/ECOG-PS (Categorical): It will be described at baseline, start of chemotherapy phase, start of post-chemotherapy phase and end of study.
- Subject autonomy (Categorical): It will be described at baseline, start of chemotherapy phase, start of post-chemotherapy phase and end of study.
- Time from initial diagnosis (Continuous): Defined as time, in months, from initial diagnosis date to informed consent date (enrolment in the study).
- Histology (Categorical)
- Initial stage (Categorical):
- Initial TNM stage (Categorical)
- Actual stage (Categorical)
- Actual TNM stage (Categorical)
- Primary tumor location (Categorical)
- Metastatic location (Yes; No) (Categorical). If affirmative:
  - Number of metastatic locations (Continuous)
  - Metastatic location (Categorical):
    - It will be provided the frequency of brain or CNS metastases (Categorical)
    - It will be provided the frequency of liver metastases (Categorical)
- Family history of cancer (Yes, No): If affirmative:

- Cancer type (Categorical)
- Relative degree per cancer type (Categorical)

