#### Endpoints analyzed:

- Progression-free survival (PFS): The PFS analysis will be based on the programmatically derived RECIST 1.1 using the Investigator tumor assessments. The analysis will be performed using Kaplan Meier plots. Summaries of the number and percentage of patients experiencing a PFS event will be provided along with median PFS and its 95% confidence interval. In addition, the proportion of patients who are progression-free at 6 (PFS 6) and 12 (PFS 12) months will be presented.

A subgroup analysis may be conducted comparing PFS in the following subgroups, assuming sufficient sample size per subgroup: platinum therapy receiving (carboplatin or cisplatin), age ( $\geq 65$ ,  $< 65$ ), gender, performance status, smoking status, CNS metastasis at baseline (Yes/No) and number of chemotherapy cycles (5 or 6 cycles vs 4 or less cycles)

For each subgroup, the HR and 95% CI will be calculated by Cox regression and a log-rank test will be provided.

- Objective response rate (ORR): The ORR will be based on the programmatically derived RECIST 1.1 using the investigator tumor data. Summaries will be produced that present the number and percentage of patients with a tumor response (CR/PR). 95% CI will also be presented.

A subgroup analysis may be conducted comparing ORR in the following subgroups, assuming sufficient sample size per subgroup: platinum therapy receiving (carboplatin or cisplatin), age ( $\geq 65$ ,  $< 65$ ), gender, performance status, smoking status, CNS metastasis at baseline (Yes/No) and number of chemotherapy cycles (5 or 6 cycles vs 4 or less cycles). Results will be compared using Chi-Squared test.

- Duration of response (DoR): DoR will be analyzed using the investigator tumor data in responding patients. Descriptive data will be provided for the DoR in responding patients (continuous data), including the associated Kaplan-Meier curves. In addition, the DoR at 1 year (DoR 12) will be analyzed.

A subgroup analysis may be conducted comparing DoR in the following subgroups, assuming sufficient sample size per subgroup: platinum therapy receiving (carboplatin

or cisplatin), age ( $\geq 65$ ,  $< 65$ ), gender, performance status, smoking status, CNS metastasis at baseline (Yes/No) and number of chemotherapy cycles (5 or 6 cycles vs 4 or less cycles)

For each subgroup, the HR and 95% CI will be calculated by Cox regression and a log-rank test will be provided.

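### Baseline CNS metastasis is coded Yes/No although brain imaging is required only on suspicion, so never-imaged patients can pass as negative and a pre-existing lesion can be dated as progression

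*Protocol*

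**What the plan says.** **Entry.** Protocol Section 5.1, criterion 4b, accepts patients who "do not have brain metastases, or have brain metastases that are asymptomatic", as well as those with treated lesions. Its only imaging instruction for the brain is "Patients with suspected brain metastases at screening should have a CT/MRI of the brain prior to enrollment".

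**Routine coverage.** Protocol Section 8.1 describes CT or MRI "of the chest and abdomen (including the entire liver and both adrenal glands), collected during screening/baseline and at regular (follow-up) intervals during study treatment", and adds: "Any other areas of disease involvement should be additionally imaged based on the signs and symptoms of individual patients". The tumor-assessment row of the schedule (Table 1) gives timing but, in its visible text, no anatomical region.

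**Progression rule.** Appendix E, on identifying new lesions at follow-up, states that a lesion found "in an anatomical location that was not scanned at baseline is considered a NL and will indicate disease progression". PFS runs to the first objective progression or death, and the end of response for DoR is tied to the same date (Protocol Section 9.4; SAP 4.2.2.1).

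**Analysis.** Protocol Sections 9.5.1 and 9.5.2.2 list CNS metastasis at baseline (Y/N) as a subgroup factor for safety, PFS and OS. SAP 5.1 and 5.2.1 repeat it and extend it to ORR and DoR; the SAP list reads "CNS metastasis at baseline (Yes/No) and number of chemotherapy cycles". SAP 4.3.3 also reports the baseline frequency of brain or CNS metastases. Neither document has a level for patients whose brain was not imaged, or a sensitivity analysis for progression that rests on a first brain scan alone.

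**The concern.** The patients whom criterion 4b admits with silent brain disease are the ones least likely to trigger a scan under the same criterion. Two consequences follow.

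First, the No level of the CNS factor can combine patients shown to be negative with patients nobody looked at. The reported baseline frequency, and any Yes/No contrast, would then depend partly on each site's scanning habit.

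Second, a lesion that was present at entry but first seen on a later scan becomes a new lesion, and so a PFS event and, in a responder, the end of response. The first scan might be prompted by symptoms. It might also be done when prophylactic cranial irradiation is considered, which is plausible, although the documents require no scan before it. Either way the event date would reflect when someone looked, not when the disease changed.

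**Working it through.** The plan states no figure on this point, so there is nothing to reproduce. The first step compares the text; the rest sizes the effect under stated assumptions.

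**1. Does any visible passage close the gap?** Criterion 4b makes the brain scan conditional. Section 8.1 names chest and abdomen and leaves other areas to signs and symptoms. Appendix E does warn that a lesion later found in a body part not scanned at baseline counts as progression. It advises covering the sites to which the disease tends to spread and gives brain MRI or CT among its examples. For the required regions, however, it refers to Table 1, whose visible row names none. The advice is therefore not turned into a requirement.

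**2. Inputs.** N = 85 (Protocol 9.2). Median time to progression of 4 to 6 months (Protocol 2.3.3, describing the disease under platinum-based chemotherapy; used only for scale). The rest is assumed, because the documents give no rates: 13 known CNS-positive, so 85 − 13 = 72 others; 25%, 50% or 75% of the 72 not imaged; silent lesions in 5%, 10% or 20% of those.

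**3. Formulas.**
- Affected patients: n = 72 × share not imaged × share with silent lesions.
- Share of all true positives missed: n/(13 + n).
- Share of the trial: m = n/85.
- Fall in 6-month PFS: m × S(6). With exponential PFS, S(6) = 0.5^(6/median), which is 0.35 at a median of 4 months and 0.50 at 6 months.
- Dilution of a true Yes-versus-No hazard ratio: observed HR ≈ HR/[(1 − c) + c × HR], with c = n/72.

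| | Low | Mid | High |
|---|---|---|---|
| Not imaged / silent lesions | 25% / 5% | 50% / 10% | 75% / 20% |
| Patients not imaged | 18 | 36 | 54 |
| n | 0.9 | 3.6 | 10.8 |
| n/(13 + n) | 6% | 22% | 45% |
| m | 1.1% | 4.2% | 12.7% |
| Fall in 6-month PFS, points | 0.4–0.5 | 1.5–2.1 | 4.5–6.4 |
| True HR of 1.5 appears as | 1.49 | 1.46 | 1.40 |

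Mid case in full: 72 × 0.50 × 0.10 = 3.6; 3.6/85 = 4.2%; 4.2% × 0.35 = 1.5 and 4.2% × 0.50 = 2.1 points; c = 3.6/72 = 0.05, so 1.5/(0.95 + 0.075) = 1.46.

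The PFS figures are upper values for each set of inputs. They take every silent lesion to be found and called progression before month 6, in patients whose PFS is otherwise like that of the rest.

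**4. The coding matters in both directions.** In the mid case the true baseline frequency is (13 + 3.6)/85 = 19.5%. If never-imaged patients are entered as No, the table shows 13/85 = 15.3%. If they are left missing and dropped from the denominator, as SAP 5 and 6.2 direct for missing values, it shows 13/(85 − 36) = 26.5%. Neither figure is right, and the SAP does not say which would be reported.

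**The case against.** The case against has real force on several points.

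- **Appendix E addresses the mechanism.** It asks for care over baseline coverage and names the brain as an example region, so sites may well scan more than criterion 4b demands. That limits how often the problem arises. It does not tell the analyst which patients were scanned.
- **Part of the schedule may be blacked out.** The tumor-assessment row cites a footnote whose text appears to be redacted. It may or may not concern brain imaging, so the statement about Table 1 covers visible text only.
- **Miscoding is not stated.** A reader might infer that CNS status *is* misclassified. No passage says that a never-imaged patient is entered as No, and the eCRF is not among the documents. The supportable statement is that it can be.
- **The net direction for PFS is open.** A reader might infer that PFS is shortened overall. Follow-up brain imaging is also driven by symptoms, so true silent CNS progression may be found late or missed, which lengthens PFS.
- **The share affected is not the loss in PFS6.** A reader might take the mid-case 4.2% of patients as a loss of about four points. Some of those patients would have had an event by month 6 anyway, hence 1.5 to 2.1 points at most.
- **Stakes are limited.** The study is descriptive, has no hypothesis, and makes the subgroup analyses conditional on sufficient numbers. Imaging by local practice is a deliberate real-world feature.

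These points limit the size of the effect and the strength of the wording. They leave the missing category, and the missing sensitivity analysis, in place.

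**Conclusion.** The concern holds as a possibility that the current data definitions cannot rule out or measure. The two-level CNS factor can mix patients who are negative on imaging with patients never imaged. In patients without a baseline brain scan, and only in them, the new-lesion rule can bring PFS and DoR events forward; where the brain was scanned at baseline, known lesions are followed as such.

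The size is unknown. Under the mid-case assumptions about 3.6 of 85 patients are affected, 6-month PFS falls by at most about 1.5 to 2.1 points, and dilution of the subgroup hazard ratio is slight. Delayed detection of genuine CNS progression offsets this to an unknown degree. Overall primary AE incidences are untouched; only an optional safety summary split by CNS status would be affected. The change is worth making because it is cheap and the ambiguity is hard to resolve once the data are reported.

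**What to change.** No additional scans and no change to RECIST are needed.

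1. Record whether the brain was imaged at baseline, with date and modality. In SAP 4.3.3, 5.1 and 5.2.1, code CNS status as present, absent on imaging, or not imaged, and show the not-imaged group separately in the subgroup analyses. Restriction to imaged patients should be supplementary only. On the assumptions above it would drop 18 to 54 of 85 patients (21% to 64%), and because imaging is required on suspicion, those retained are selected for suspected disease. The report should say so.
2. Add one PFS/DoR sensitivity analysis for patients without baseline brain imaging. A brain lesion that is the sole evidence of progression on the first brain scan is not counted as the event. The patient is followed to the next documented progression or death, otherwise censored at the last evaluable assessment. Label the result as a bound, since some of the discounted events are true progression. Scanning may also stop after progression plus one follow-up scan, so some of these patients will simply be censored.

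The cost is one eCRF field that can be filled from records, some small cells in the subgroup tables, and one extra analysis.
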